- After progression, patients will be followed only for overall survival.
  - o In case of encorafenib and binimetinib are providing a clinical benefit to any patient, treatment could be continued after discussion with Sponsor if it agrees on that. In this case, follow up will be done as per institutional criteria. In the study, these patients will be followed only for overall survival.
- Study assessments: in each monthly visit, adverse events will be registered, blood samples will be collected for blood cell counts and general biochemistry (including magnesium, potassium and creatinine-kinases); an ECG will be performed at baseline, after one month of treatment, and every 3 months thereafter; a left ventricular ejection fraction (LVEF) evaluation will be performed by as per institutional guidelines at baseline and every 3 months thereafter ophthalmologic anamnesis and evaluation will be performed by oncologist at baseline and in every monthly visit, if there's any alarm symptom or sign, patient will be evaluated by Ophthalmologist. Body CT-scan and contrast enhanced brain MRI will be performed baseline and every 8 weeks up to 12 months and according to normal practise thereafter. More information regarding study determination is provided in section 8 of this protocol.

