#### Non-radiological Assessments

Visible cutaneous lesions must be measured clinically. Digital and standardized photographic images including a ruler for scale as part of the image are recommended for documentation. All clinical assessments must be performed within proximity (± 7 days) of any protocol specified radiographic assessments

**Safety evaluation:** Safety assessments and adverse events include tumour-related, unrelated and treatment-related signs and symptoms. Adverse events will be documented and recorded in the CRF upon patient notification. AEs will be collected from the signing of Informed Consent until the end of treatment visit (30 days after end of treatment) or up to resolution. Classification of toxicity will be done according to the common terminology criteria for adverse events of the National Cancer Institute, version 4.03 (NCI CTCAE v. 4.03).

**PFS follow-up:** Body CT-scan and contrast enhanced brain MRI will be performed baseline and every 8 weeks (+/-1 week) up to 12 months and according to normal practice thereafter **until disease progression**, **independently of the end of treatment reason if it was not the documentation of disease progression**.

**OS Follow-up:** After disease progression all patients will be monitored to determine subsequent antineoplastic treatments and survival. It is recommended to maintain contacts by phone or by other methods every 4 weeks to carry out timely follow-up (up to 24 months or study closure).

**New anti-cancer therapy:** Information on subsequent treatments should include the list of post-treatment treatments, the drugs administered, and the date of initiation and discontinuation of each drug. All data will be recorded in the medical record and in the eCRF.

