# 10.2. Study endpoints

Intracranial objective response (iORR) rate by modified RECIST 1.1 before local treatment in cohort 1 and 2: iORR calculated as the proportion of patient with a best overall intracranial response of complete response (CR) or partial response (PR) before local treatment in cohort 1 and 2. The final statistical analysis of this endpoint is expected to be performed within 3 months after the local treatment of the last patient in any cohort. iORR will be also reported separately for both cohorts.

**Duration of intracranial response in both cohorts (iDOR):** Calculated as the time from the date of first documented CR or PR to the first documented intracranial progression or death due to underlying cancer, in patients with documented intracranial CR or PR before local treatment. The final statistical analysis of this endpoint is expected to be performed within 6 months after database closure expected at 24 months after last patient inclusion, however interim analysis might be performed when analysing other primary variables.

The intracranial progression free survival (iPFS) by modified RECIST in both cohorts: iPFS is defined as the time from the date of inclusion to the date of the first documented intracranial disease progression or death due to any cause, whichever occurs first. PFS will be determined based on tumour assessment (modified RECIST version 1.1 criteria). The local Investigator's assessments will be used for analyses. Those patients who are alive and have not progressed at the last follow-up, date of progression will be censored at the date of the last follow-up. Patient with no additional image test other than baseline will be censored to the day after to inclusion. The final statistical analysis of this endpoint is expected to be performed within 6 months after database closure expected at 24 months after last patient inclusion, however interim analysis might be performed when analysing other primary variables.

Percentage of patients free of intracranial progression at 6 (week 24), 12 (week 48) and 24 months (week 96) in both cohorts: percentage of patients free of intracranial progression assessed by modified RECIST at 6 months (week 24), 12 months (week 48) and 24-month (week 96) considering date of inclusion. The final statistical analysis of this endpoint is expected to be

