# **Table 14: Overall Response Assessment (RECIST)**

Target Lesions	Non-target Lesions	New Lesions	Overall Response	
CR	CR	No	CR	
CR	Non-CR/non-PD	No	PR	

CR	Not evaluated	No	PR
PR	Non-PD or not all evaluated	No	PR
SD	Non-PD or not all evaluated	No	SD
Not all evaluated	Non-PD	No	NE
PD	PD Any		PD
Any	PD	Yes or No	PD
Any Any		Yes	PD

CR = complete response, PR = partial response, SD = stable disease, PD = progressive disease, and NE = not evaluable

Disease progression and response evaluations for intracranial and extracranial disease will be determined according to the definitions established in the Response Evaluation Criteria in Solid Tumours (RECIST 1. 1); Minor modifications will be applied to the assessment of intracranial lesions:

Intracranial response assessment: The Investigator modified RECIST 1.1 criteria will be used to evaluate the intracranial response. The modifications to RECIST 1.1 impact the number and the minimal size of the target lesions selected at baseline. Up to 5 intracranial lesions should be selected as target; based on size and evaluation/tracking feasibility. All the remaining brain lesions different from these 5 target lesions must be considered as non-target lesions (independently of their size). The size of target and non-target lesions must be measured. Measurable lesions are defined as those that can be accurately measured in at least one dimension with the longest diameter  $\geq 5$  mm when evaluated by contrast-enhanced MRI.

For intracranial response, target lesions as small as 5 mm may be selected, however the scanning should be in accordance with modified RECIST 1.1 (contiguous slices of maximum thickness corresponding to half the size of the lesion.

Contrast-enhanced MRI is the only modality accepted for the assessment of intracranial lesions. For justified exceptions please, contact with the sponsor:

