# 4.6. INTRACRANIAL PROGRESSION-FREE SURVIVAL (IPFS).

Intracranial Progression-free survival (PFS), defined as the time from inclusion (first dose of treatment) until intracranial tumour progression (RECIST 1.1) or death. Patients without any of the previous events are censored at the date of the last available tumor assessment.

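### The protocol censors iPFS at an undefined last follow-up and the SAP at the last tumour assessment; one rule tied to the last brain MRI is needed

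*Combined protocol and SAP*

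**What the plan says.** Protocol 10.2 defines the iPFS event as "the first documented intracranial disease progression or death due to any cause, whichever occurs first". It adds that "PFS will be determined based on tumour assessment (modified RECIST version 1.1 criteria"). For patients who are alive and have not progressed, the "date of progression will be censored at the date of the last follow-up". The next sentence reads: "Patient with no additional image test other than baseline will be censored to the day after to inclusion".

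SAP 4.6 gives a different date for the same endpoint: "Patients without any of the previous events are censored at the date of the last available tumor assessment". SAP 4.7 uses the same sentence for extracranial PFS (ePFS).

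Four other provisions bear on what a last follow-up can be:

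- **Imaging schedule (protocol 8.1).** CT and brain MRI are done "every 8 weeks (+/-1 week) up to 12 months and according to normal practice thereafter".
- **After progression (protocol 5.3).** "After progression, patients will be followed only for overall survival". At the first evaluation this applies to progression in the brain, the body, or both. In Table 11 the column for follow-up after progression lists only survival and new anticancer therapy, with no brain MRI. Protocol 8.1 recommends survival contact every 4 weeks, by telephone or other means.
- **After a switch of treatment (protocol 8.2 f).** Only the date of death is recorded.
- **Modality (protocol 10.3.1).** "Contrast-enhanced MRI is the only modality accepted for the assessment of intracranial lesions".

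**The concern.** One endpoint has two censoring dates. They differ most in patients who are alive, have no documented intracranial progression and no longer have planned brain MRI: chiefly those with extracranial progression first, and those who switched treatment. Patients followed beyond month 12 on a sparser local schedule are affected too. If last follow-up means last contact of any kind, months or years in which the brain was not imaged count as intracranially progression-free time.

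That sits badly with the rest of the paragraph. A patient with no image after baseline gets one day of credit, whereas a patient with one later MRI followed by survival contact alone gets credit up to the last contact.

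The landmarks most exposed are 12 and 24 months. Freedom from intracranial progression at both is a named secondary objective (protocol 4.2). The SAP's main iPFS tables stop at 12 months, but 24-month iPFS appears in SAP 7.2 and in the additional table by radiotherapy.

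**Working it through.** No figure in the documents depends on this rule, so there is nothing to reproduce first. The check is one of direction, then of size on assumed inputs.

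**1. Direction.** The Kaplan-Meier estimate is S(t) = product over event times j of (1 − d_j/n_j). Take a patient alive without intracranial progression, with last MRI at time m and last contact at time c > m. Censoring at c keeps the patient in n_j for every event between m and c; censoring at m does not. Deaths and documented progressions, and so all d_j, are the same under both rules. Each n_j is therefore equal or larger under last follow-up, and S(t) is equal or higher. This follows from the definitions alone.

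**2. Size, first set of assumptions.** 1,500 simulated trials of 63 patients with exponential times. MRI every 8 weeks until extracranial progression. Median time to intracranial progression 8 months and to extracranial progression 9. Follow-up 24 to 60 months (36 months of recruitment plus 24 of follow-up, protocol 8.3).

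| Assumed median survival after progression | 12-month iPFS: last follow-up / last assessment | Difference | 24-month iPFS: last follow-up / last assessment | Difference |
|---|---|---|---|---|
| 8 months | 36.5 / 35.6% | 0.9 | 12.5 / 10.2% | 2.3 |
| 15 months | 42.4 / 39.4% | 3.0 | 21.5 / 14.9% | 6.6 |
| 25 months | 46.3 / 40.9% | 5.4 | 28.4 / 17.0% | 11.4 |

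**3. Size, second set.** 200,000 patients per scenario. MRI every 8 weeks to about month 12, then every 16 weeks (assumed), stopping at extracranial progression. The range of 5.6 to 11 months for each progression time is taken from the two PFS medians in protocol section 3. Survival times are assumed.

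| Medians in months: intracranial PD, extracranial PD, death without PD, PD to death | 12 months: last follow-up / last MRI | 24 months: last follow-up / last MRI | Median iPFS, months | Censored |
|---|---|---|---|---|
| 5.6, 11, 30, 9 | 22.5 / 21.5% | 7.0 / 5.3% | 5.52 / 5.52 | 2.3% |
| 5.6, 11, 30, 18 | 27.1 / 23.8% | 13.4 / 8.0% | 5.52 / 5.52 | 7.0% |
| 8, 8, 30, 18 | 37.4 / 33.3% | 20.4 / 12.7% | 7.36 / 7.36 | 10.8% |
| 11, 5.6, 30, 18 | 46.2 / 41.2% | 27.2 / 17.1% | 10.63 / 9.20 | 14.6% |
| 11, 11, 60, 24 | 48.7 / 44.4% | 29.3 / 19.4% | 11.04 / 10.42 | 17.2% |

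The differences are 1.0 to 5.0 points at 12 months and 1.7 to 10.1 at 24 months. The median is unchanged in three scenarios and longer by 0.6 and 1.4 months in the other two. Among censored patients the mean gap between last MRI and last contact is 25 to 31 months.

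**4. What last-MRI censoring leaves.** The first set was rerun with 400,000 patients per scenario, adding a hypothetical benchmark in which 8-weekly brain MRI continues after extracranial progression. In the same order of assumed survival:

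- 12 months: last MRI 35.7, 40.2, 41.5%; benchmark 29.6, 33.1, 35.0%. Remaining gap 6.1, 7.1, 6.5 points.
- 24 months: last MRI 10.2, 15.2, 17.4%; benchmark 5.6, 7.7, 9.2%. Remaining gap 4.6, 7.5, 8.2 points.

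Intracranial progression that occurs after MRI stops goes unseen, and the patient is then either censored or counted only at death. No censoring date recovers that information.

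**The case against.** Much of the case on the other side stands.

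- **The SAP governs the detail.** Protocol 10.6 says full analysis details will be in the SAP, and the SAP rule is already based on tumour assessment. A reader might infer that nothing indicates which document prevails; that goes too far. The inflation arises only if the protocol wording is applied literally.
- **Last follow-up may mean imaging follow-up.** Protocol 8.1 describes PFS follow-up (CT and MRI) separately from OS follow-up (contact), and the sentences around the rule concern imaging. A reader might infer that the protocol definitely runs iPFS to the last telephone call. It does not say so: the term is undefined, and the protocol also uses follow-up for survival contact. It is equally unclear whether a patient with extracranial progression counts as not progressed. If not, the protocol has no censoring rule for that patient.
- **A body CT date is an edge case.** The SAP wording would allow it, but protocol 10.3 and 10.3.1 tie intracranial assessment to contrast-enhanced MRI, and CT and MRI share the same visits to month 12.
- **The sizes are not estimates for this trial.** Assumed survival after progression of 15 to 25 months exceeds the historical median survival of about 9 months in protocol 2.3. At 8 months the differences are 0.9 and 2.3 points.

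The SAP text mentions database closure with 4 patients still on treatment, and 0 patients censored at time 0. A reader might infer that the rule was picked with results in view. These remarks show that some data were known when that text was written, and they fit an imaging-based rule. They do not show that a choice was made on results.

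**Conclusion.** The concern holds as an inconsistency with a known direction and an uncertain size. The two documents give different censoring dates, and the protocol date, read literally, conflicts with the imaging basis of its own paragraph. That reading cannot lower iPFS. Increases of roughly 1 to 5 points at 12 months and 2 to 11 at 24 months rest on assumed progression and survival rates and on MRI stopping at extracranial progression; only the direction follows from the documents.

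The consequence is limited. iPFS is a secondary endpoint with no formal hypothesis, and deaths are events under both rules. The SAP rule is preferable but should name the brain MRI. It would be wrong to infer that adopting it makes iPFS unbiased: in the benchmark comparison at 12 months, more upward bias remains (about 6 to 7 points) than the change of rule removes (about 1 to 5).

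**What to change.** Amend protocol 10.2 to match the SAP, and state in both documents that patients without intracranial progression or death are censored at the date of the last adequate contrast-enhanced brain MRI. For ePFS, name the last body tumour assessment in the same way.

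State in the report that censoring at extracranial progression may be informative because planned brain MRI stops there, and give the number of patients censored for that reason. If the protocol can no longer be amended, report the rule that was used and show the other as a sensitivity analysis.

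The cost is one sentence in each document and one extra count in the report, with no new data collection. Late iPFS estimates will be less favourable than under the literal protocol reading, and some upward bias may remain.

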# 10. STATISTICS

# 10.1. Sample size calculation

# Sample size calculation:

The sample calculation has been done for the **initially proposed primary endpoint (cohort 1)** and it's based on a Fleming's Single Stage Procedure:

We want to show that the Intracranial response rate by modified RECIST 1.1 before local treatment is superior or equal to the reference value, say, 90=40%. Under the hypothesis to have a response rate under new treatment ( $\pi$ 1) of 60% with  $\alpha$  risk = 5% in one-sided test and a power of 80%, the required sample size is 38 patients.

Finally, assuming that, 20% of patients will be lost of follow up, die or progress before day 56 without doing the first tumour assessment (according data published in COMBI-MB study), the initial sample size will be 48 patients, to obtain 38 evaluable patients.

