# 3. RESULTS

# 3.1. RECRUITED PATIENTS

All baseline characteristics will be performed using the ITT and PP population. In order to report the main efficacy analysis, also both the ITT and PP population will be used, meanwhile the secondary efficacy endpoints will be analyzed using the PP population. Finally the safety population will be used to report the safety results.

Table 8: Patients recruited by Hospital

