# 4.6.1.ITT ALL PATIENTS: INTRACRANIAL PROGRESSION-FREE SURVIVAL (IPFS).

0 patient has been censored at time 0 due to lack of tumor assessments.

Table 72: iPFS (event). ITT All patients

PFS (event)	N	%	95%CI
Censored			
Event (PD/death)			
Total			

Table 73: Median iPFS. ITT All patients

	Median	95%CI
PFS		

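### For patients who die without a post-baseline scan, protocol 10.2 contradicts its own iPFS definition and SAP 4.6: one sentence censors them on the day after inclusion, the others count the death as an event

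*Combined protocol and SAP*

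**What the plan says.** **Protocol 10.2, iPFS.** The event definition is inclusive and covers death whatever its cause. It opens: "iPFS is defined as the time from the date of inclusion to the date of the first documented intracranial disease progression or death due to". The general censoring sentence is confined to living patients without progression and dates their censoring at last follow-up. It begins: "Those patients who are alive and have not progressed at the last follow-up, date of progression will be censored at the date of the last". The next sentence reads: "Patient with no additional image test other than baseline will be censored to the day after to inclusion". It selects patients by scan status alone. It does not mention vital status and sets no time limit.

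**SAP 4.6.** The endpoint runs "until intracranial tumour progression (RECIST 1.1) or death", and "Patients without any of the previous events are censored at the date of the last available tumor assessment". SAP 4.6.1 (ITT, all patients) adds: "0 patient has been censored at time 0 due to lack of tumor assessments".

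**Populations.** SAP 3.1 says "meanwhile the secondary efficacy endpoints will be analyzed using the PP population", and SAP section 2 admits a patient to PP only with a baseline and a first assessment. SAP 4.6.1 to 4.6.3 nevertheless also tabulate iPFS for ITT, overall and by cohort.

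**How many might lack a scan.** The first post-baseline MRI falls after 56 days of treatment. Protocol 10.1 plans for the possibility that "20% of patients will be lost of follow up, die or progress before day 56 without doing the first tumour assessment".

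**The concern.** A death before the first MRI is among the clearest treatment failures this trial can record, and it is what including death in the iPFS definition is meant to capture. Read as written, the no-scan sentence overrides that definition for exactly these patients. They leave the risk set on day 1 and contribute no event.

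The censoring would be informative and could act in only one direction: the ITT curve, its median and its landmark percentages would all rise. The SAP treats the same patient as an event, so two analysts working from the two documents could produce different ITT results from the same data. SAP 4.6.1 counts time-0 censorings for lack of assessments, but SAP 4.6 has no explicit no-scan rule that says whether deaths are exempt.

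**Working it through.** **1. The rules side by side**

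| Patient | Protocol 10.2: definition and general censoring sentence | Protocol 10.2: no-scan sentence, literal | SAP 4.6 |
|---|---|---|---|
| Dies, no post-baseline scan | Event at death | Censored day after inclusion | Event at death |
| Alive, no post-baseline scan | Censored at last follow-up | Censored day after inclusion | Censored at last assessment, which is baseline |
| Scanned at least once, then dies | Event | Not covered | Event |

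The first row is the substantive conflict. In the second row, the no-scan sentence and the SAP both place censoring at essentially the start of follow-up.

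**2. The plan's own figures**

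Protocol 10.1 gives response rates of 40% and 60%, one-sided 5% and power 80%. The normal approximation for a single-stage design gives n = [(1.645·√(0.4·0.6) + 0.842·√(0.6·0.4)) / 0.2]² = 37.1, rounded up to 38. Allowing for 20% without a first assessment, 38/0.8 = 47.5, rounded up to 48. Both stated figures reproduce. The 20% corresponds to 0.20 × 48 = 9.6 patients in cohort 1, or 0.20 × 63 = 12.6 if applied to everyone. It pools loss to follow-up, death and progression, and the share due to death is not given.

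**3. Size of the bias if the sentence is applied literally**

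The documents state no expected iPFS, so a curve has to be assumed: exponential with median 5.6 months. That is the PFS figure quoted in the trial rationale (protocol section 3) for the asymptomatic cohort of the dabrafenib-trametinib brain-metastasis trial.

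- True curve: S(t) = 0.5^(t/5.6), so S(6) = 47.6% and S(12) = 22.6%.
- Let d be the share of patients who die before day 56 without a scan. Censoring them on day 1 leaves a fraction 1 − d at risk, so after day 56 the Kaplan-Meier estimate is about S(t)/(1 − d).
- The apparent median solves S(t) = 0.5(1 − d), which gives t = 5.6 × [1 + log₂(1/(1 − d))].

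| d | 6-month iPFS | 12-month iPFS | Median (months) |
|---|---|---|---|
| 0 | 47.6% | 22.6% | 5.6 |
| 2% | 48.6% | 23.1% | 5.8 |
| 5% | 50.1% | 23.8% | 6.0 |
| 10% | 52.9% | 25.2% | 6.5 |
| 20% (upper bound) | 59.5% | 28.3% | 7.4 |

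Under the assumed curve, 1 − S(56 days) = 20.4% of patients progress or die before day 56. The last row therefore requires nearly every early failure to be a death without a scan.

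**4. Check by simulation**

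Trials were simulated 2,000 times per setting, with follow-up cut at 24 months. For N = 48, mean 6-month iPFS moved from 0.474 to 0.484 with 1 early death censored on day 1, from 0.472 to 0.504 with up to 3, from 0.477 to 0.532 with up to 5, and from 0.477 to 0.584 with up to 10. For N = 63 with up to 13, it moved from 0.477 to 0.585. These agree with the formula.

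**The case against.** There is a good case that this is only loose drafting. The no-scan sentence directly follows one confined to living patients without progression, and it can be read as supplying the censoring date for those patients when no scan exists. Protocol 10.6 leaves full analysis details to the SAP, and SAP 4.6 gives the handling one would want. The supplementary table of iPFS by radiotherapy also lists death without prior progression as a category separate from censoring. The SAP count of patients censored at time 0 is zero. PP patients cannot trigger the rule, since each has a first assessment. iPFS is a descriptive secondary endpoint, and the trial's success criterion is response rate.

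Most of this stands, and it limits the point to an inconsistency to be reconciled. It does not remove it. The sentence carries no limit to living patients, and neither document says how unscanned deaths are classified when the rule is used. The zero fits two situations equally well: nobody went unscanned, or unscanned deaths were counted as events. It could also be template text.

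A reader might infer more than the documents support:

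- **That reported iPFS is biased.** This would hold only if the literal protocol sentence governed, and the SAP rule points the other way.
- **That the bias is about 12 percentage points.** This treats the whole pooled 20% as unscanned deaths. Part of it is loss to follow-up and part is progression.
- **That the bias distorts a comparison with a 5.6-month benchmark.** The trial rationale contrasts 5.6 months with 11 months in another trial as background. It sets no iPFS target for this trial.

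**Conclusion.** Protocol 10.2 is inconsistent with itself and with SAP 4.6 for one class of patient: those who die with no post-baseline scan. If the literal sentence were followed, ITT iPFS would be biased upwards. Under the assumed exponential curve with a 5.6-month median, 6-month iPFS would rise by nothing at d = 0, about 1 percentage point at 2%, 2.5 at 5% and 5.3 at 10%, with 11.9 as an upper bound at 20%. The median would lengthen by 0 to 1.8 months over the same range. This is a range under an assumption, not an estimate for this trial, because d is unknown and 5.6 months is described as PFS, not intracranial PFS.

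Under SAP 4.6 the bias is nil. PP iPFS is unaffected by the choice of rule; that PP leaves out early deaths altogether is a separate matter. The primary response endpoint is not touched. The zero count suggests that few or none were affected in practice. The wording should be fixed, but it does not threaten the trial's main conclusion.

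**What to change.** In protocol 10.2, limit the no-scan sentence to living patients, for example: *Patients who are alive and have no post-baseline tumour assessment are censored on the day after inclusion; a death before the first assessment is an iPFS event on the date of death.* Put the same rule in SAP 4.6, so that the time-0 count in 4.6.1 rests on a stated definition. Under Table 72, the ITT iPFS event table, report the number of unscanned deaths counted as events beside the number of living patients censored for want of a scan.

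The cost is one sentence in each document and one line in a table. Dates of death are already collected for overall survival, so no new data are needed. Compared with a literal application of the protocol sentence, ITT iPFS may come out slightly less favourable. If no patient died unscanned, nothing changes.
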